## LIST OF ABBREVIATIONS

ABBREVIATION	DEFINITION
AE	adverse event
BID	bis in die; two times per day
BRIEF	Behavior Rating Inventory of Executive Function
CBD	whole blood cannabidiol
CRF	Case Report Form
C-SSRS	Columbia-Suicide Severity Rating Scale
DS	Dravet syndrome
ECG	electrocardiogram
EDA	electrodermal activity
EmB	Embrace treatment population
EMBRACE	Empatica Embrace watch system
EOS	end of study
EQ-5D-5L	standardized measure of health status
ERT	Seizure Diary custom built by ERT
ET	Early Termination
EU-REACH	European Union Registration, Evaluation, Authorisation and Restriction of Chemicals
GCP	Good Clinical Practice
HADS	Hospital Anxiety and Depression Scale
ICH	International Conference on Harmonization
IDSMC	Independent Data and Safety Monitoring Committee
IEC	Independent Ethics Committee
IPCAB	International Pediatric Cardiology Advisory Board
IRB	Institutional Review Board
LED	light-emitting diode
MMRE	mixed model repeated measures
OLE	open-label extension
PSS	Perceived Stress Scale
QoL	Quality of Life
SAF	safety analysis population
SMEI	Severe Myoclonic Epilepsy Of Infancy
SUDEP	Sudden Unexpected Death in Epilepsy
THC	tetrahydrocannabinol
ULN	upper limit of normal
USA	United States of America
ZX008	Fenfluramine Hydrochloride Oral Solution

## STUDY SYNOPSIS

Study Title: An Exploratory, Pilot Study to Assess the Usability of the Embrace Seizure Detection Watch in Children and Young Adults with Dravet Syndrome: A Sub-study to the ZX008-1503 Open-Label Extension Trial	
Study Number: ZX008-1503-SS01	
Study Product: Fenfluramine Hydrochloride, ZX008	
Type of Study: Exploratory	Indication Studied: Dravet syndrome
Phase of Development: III	Countries: North America
Sponsor: Zogenix International Limited	
Coordinating Investigator: 

 Institute of Neurology and Neurosurgery at St. Barnabas Research Department Livingston, New Jersey USA	
Estimated Duration of Individual Subject Participation: The duration of the study for an individual subject is expected to be approximately 12 weeks with the option to extend to 24 weeks.	
Objectives: The primary objective of the study is: 
 
• To assess the overall usability and performance (correct use and ease of use) of the Empatica Embrace Seizure Detection watch system (Embrace) in outpatients with Dravet syndrome.
 
 The secondary exploratory objectives of the study are: 
 
• To compare objective convulsive seizure count, as captured by the Embrace, to convulsive seizure count captured manually in the seizure diary.
 
• To compare objective convulsive seizure count during periods of sleep, as captured by the Embrace, to convulsive seizure count during periods of sleep captured manually in the electronic seizure diary.
 
• To examine if the size of the electrodermal activity (EDA) response during and after a convulsive seizure is reduced over time with the ZX008 treatment.
 
• To examine if skin-surface temperature changes with ZX008 treatment.
 
• To examine if skin-surface temperature levels are different during periods of time preceding convulsive seizures than during times that are seizure-free.
 
• To examine correlation of study drug dose and fever-induced convulsive seizure frequency, severity, and duration.
 
• To examine the timing of diary-reported events vs. automatically detected events.
 
• To assess quality of life while using the Embrace system with the following measures:             
 
- Quality of Life (QoL) of the parent/caregiver using the EQ-5D-5L scale.
 
- Affective symptoms of the parent/caregiver using the Hospital Anxiety and Depression Scale (HADS).
 
 
 
• To assess caregiver stress using the Perceived Stress Scale (PSS).
 
	

**Methodology:** This is a sub-study to the ZX008-1503 OLE study. All participants in this sub-study will have participated in Study ZX008-1501 or ZX008-1504 Cohort 2 and then continued in Study ZX008-1503, which is a multicenter, open-label, long-term safety study of ZX008 (fenfluramine hydrochloride) in pediatric and young adult subjects with Dravet syndrome. The main Study ZX008-1503 consists of a 12-month OLE Treatment Period and a 2-week Post-Dosing Period. Details of dose and dose-adjustments are described in the main Study ZX008-1503.

This sub-study will include up to 20 participants who meet the entry criteria for the main Study ZX008-1503 and who are willing to wear the Embrace watch and use the Embrace system per the user instructions for 12 consecutive weeks. Those invited to participate will undergo all procedures included in the main Study ZX008-1503 during their participation in this sub-study, plus any additional procedures specific for the sub-study. At the conclusion of the sub-study, participants will revert to only using the ERT seizure diary for the remainder of their participation in the main Study ZX008-1503. Efficacy analyses for sub-study participants that rely on the ERT seizure diary or that are specific to the Embrace watch will not be included in the main ZX008-1503 analyses.

At the time of consent for the main Study ZX008-1503, subjects will also be presented with the consent for this sub-study. Subjects who consent for the sub-study will be fitted with an Embrace watch at Study Visit 1. Subjects (and/or parents/caregivers) will also be given instructions on how to use the Embrace system. The Alert app must be running on the provided iPod touch and remain in close proximity of the patient. However, parents/caregivers will continue to use the ERT seizure diary to record the number/type of seizures, rescue medications, and study drug administration.

At pre-determined assessment times, parents/caregivers will complete questionnaires specific for the sub-study, including the Ease of Use Questionnaire and the Perceived Stress Scale (PSS), to measure user experience.

**External Committees:** The ZX008 clinical program will employ an Independent Data and Safety Monitoring Committee (IDSMC) that will be responsible for safety oversight. A separate International Pediatric Cardiology Advisory Board (IPCAB) will monitor the cardiac safety of the ZX008 clinical trials.

**Number of Subjects:** Up to 20 subjects will be enrolled from the main Study ZX008-1503.

**Inclusion Criteria:** Subject must meet all of the entry criteria for the main Study ZX008-1503 to be eligible for the sub-study. In addition to meeting the above listed criteria, subjects in the sub-study must also be willing to wear and use the Embrace watch and parents/caregivers must be willing to use the Alert app per the user instructions. This includes:

1. Subject is willing to wear the Embrace watch on the wrist (alternatively ankle, if needed for younger children). Subjects are asked to wear the watch for as many hours of the day as possible, and for the entire night, if possible, for the 12-week duration of the sub-study.
2. Subject's parent/caregiver is willing to use the Alert App and receive voice and SMS notifications on their personal smart-phone, and ensure the smart-phone has internet connectivity; iOS 8.2 or higher is required for iPhone users.
3. Subject/subject's caregiver is willing to ensure that the Embrace watch remains within close proximity of the paired iPod Touch running the Empatica Alert app.

4. Subject/subject's caregiver is willing to ensure that the Embrace system is properly stored when not in use, and is not left exposed to direct sunlight, moisture, humidity or rain while in storage. The Embrace watch is water resistant but should never be submerged in water. Bathing and/or showering with the watch is acceptable, however.
5. Subject/subject's caregiver is willing to regularly clean the Embrace watch, routinely inspect the watch for sharp edges and damage, and ensure the watch is never worn over damaged or broken skin.
6. Subject/subject's caregiver is willing to ensure that the Embrace system is properly charged daily during a time when the subject is being observed so any seizures that occur during times that the device is not being worn are able to be added to the record manually.

**Exclusion Criteria:** Subjects meeting any of the exclusion criteria for main Study ZX008-1503 are not eligible for the sub-study. In addition, subject must not be enrolled into the sub-study if:

1. Subject has a known hypersensitivity to any of the Embrace device materials.
2. Subject has a clinically significant condition, or has had clinically relevant symptoms or a clinically significant illness in the 4 weeks prior to Visit 1, other than epilepsy, that would negatively impact study participation, collection of study data, or pose a risk to the subject.

**Study Product, Dose, and Mode of Administration:**

ZX008: supplied as an oral solution in a concentration of 2.5 mg/mL. Subjects will be titrated to an effective dose beginning with 0.2 mg/kg/day (maximum: 30 mg/day). Study medication will be administered twice a day (BID) in equally divided doses with food.

Empatica Embrace watch system (Embrace)/Embrace Alert app: The noninvasive Embrace wrist-worn monitoring device, reads physiological data (EDA, skin temperature, and motion) from the surface of the skin and can transmit it wirelessly to a receiver. The watch is used in conjunction with the Embrace Alert app. The Alert app detects events from user physiology, such as convulsive seizures, and sends an alert to a caregiver via a phone call or text message. The Alert app runs on an iPod Touch and must remain in close proximity of the patient.

**Duration of Treatment:** Subjects will be permitted to participate in the sub-study for the initial 12 weeks of participation in the main OLE study (ZX008-1503). Subjects may have the opportunity to extend participation in the sub-study for up to 24 weeks.

**Criteria for Evaluation:**

Safety:

Safety criteria are identical to those in the main Study ZX008-1503 and include AEs, laboratory safety parameters (hematology, chemistry, urinalysis), vital signs (blood pressure, heart rate, temperature, and respiratory rate), physical examination, neurological examination, 12-lead ECGs, Doppler ECHOs, and body weight.

Efficacy:

The primary criteria for evaluation in the sub-study is the change over time in the 5-point Likert Ease of Use Questionnaire to measure user experience.

Secondary exploratory efficacy criteria for evaluation include change over time in the following:

- Perceived Stress Scale (PSS) to measure caregiver burden.
- Correlation of monthly (28-day) convulsive seizure count between the Embrace watch and seizure diary.
- Size of EDA response during and in the post-ictal hour of convulsive seizures.
- Skin-surface temperature (measured on wrist).
- Frequency of fever-related convulsive seizures.
- Comparison of convulsive seizure count during periods of sleep, and during the combined titration and maintenance periods, between the Embrace watch and seizure diary.
- Correlation of convulsive seizure time and classification as determined by Embrace watch and seizure diary.
- EQ-5D-5L to measure quality of life of the parent/caregiver while using the Embrace.
- HADS to measure affective symptoms of the parent/caregiver while using the Embrace.

All other efficacy criteria are identical to those in the main Study ZX008-1503.

**Sample Size Determination:** This sub-study is designed as a pilot exploratory study to provide preliminary information on the ease of use of the Embrace watch to detect seizures in outpatients with Dravet syndrome, therefore, the sample size is based more on feasibility than on power to detect differences.

**Statistical Methods:**

All safety data will be summarized as described in the ZX008-1503 protocol and associated Statistical Analysis Plan. Efficacy analyses for sub-study participants that rely on the ERT seizure diary or that are specific to the Embrace watch will not be included in the main ZX008-1503 analyses. Exploratory data for the Embrace watch system data will be processed as follows:

- Embrace's automated convulsive seizure detection results will be manually compared to the diary counts of convulsive seizures. Cohen's Kappa values will be computed for agreement.

- The above will be repeated separately for events during periods of sleep vs. events while awake, based on Embrace’s determination of sleep/wake (periods of sleep will be based on actigraphy and EDA as measured by the Embrace watch).
- For each seizure detected by the Embrace watch, the peri-ictal EDA recording will be segmented from 60 minutes before detected seizure onset to 120 minutes afterward. A “significant EDA response” is declared when an increase in skin conductance level of more than 2 times the standard deviation of the pre-ictal baseline occurs. Significant EDA responses will be analyzed in terms of the amplitude of their EDA\_peak, the response duration, defined as the difference between “EDA\_end” and “EDA\_start,” and the natural logarithm of the area under the curve (AUC) of the rising phase (from “EDA\_start” to “EDA\_peak”) and of the total response (from “EDA\_start” to “EDA\_end”), ie, LogAUCrise and LogAUCtot. These measures will be examined to see if they vary over time with the treatment.
- Skin-surface temperature changes will be averaged daily and compared over time, with separate comparisons made for “seizure-free” periods and for “pre-seizure periods.” The duration of these periods will be based on average 60-minute intervals, but may also be examined with shorter intervals.
- Each episode of fever, defined as any body temperature above 98.6°F (37°C), and number, severity, and duration of each seizure detected by Embrace will be correlated to dose of study drug.

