### 1.2 RATIONALE FOR CURRENT SUB-STUDY, ZX008-1503-SS01

This is a sub-study to the ZX008-1503 OLE trial, which will include up to 20 participants who are enrolled in Study ZX008-1503. This is an exploratory sub-study to provide preliminary information on the overall usability and performance of the Empatica Embrace watch system (Embrace) in outpatients with Dravet syndrome.

Seizure frequency is the primary outcome measure for individual treatment and for clinical trials. The current gold standard for demonstrating efficacy of new anti-epileptic drugs is a 50% reduction in seizure frequency. This efficacy standard is based on patients or their caregivers maintaining seizure diaries.

Use of sensitive seizure detection technology may allow greater accuracy in seizure counting. Seizure detection technology may also provide means to address specific clinical questions, such as the occurrence of unwitnessed seizures during periods of sleep.

The Embrace has been designed for automated convulsive seizure detection and characterization. The Embrace watch monitors electrodermal activity (EDA) and accelerometer-sensed changes in motion to analyze the information and detect patterns that are typically observed in convulsive seizures in real-time. The data can then be used to compare seizure detections, false alarms, and seizures that are not detected, to e-diary seizure report information.

This sub-study for patients enrolled in the open-label extension study may provide insights into seizure triggers, such as temperature, or facilitate seizure counts during sleep and allow for comparison of various endpoints captured by the Embrace to the same endpoints captured in an electronic hand-held seizure diary.

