### **2.2 SECONDARY OBJECTIVES**

The secondary exploratory objectives of the study are:

- To compare objective convulsive seizure count, as captured by the Embrace, to convulsive seizure count captured manually in the electronic seizure diary.
- To compare objective convulsive seizure count during periods of sleep, as captured by the Embrace, to convulsive seizure count during periods of sleep captured manually in the electronic seizure diary.
- To examine if the size of the electrodermal activity (EDA) response during and after a convulsive seizure is reduced over time with ZX008 treatment.
- To examine if skin-surface temperature changes with ZX008 treatment.
- To examine if skin-surface temperature levels are different during periods of time preceding convulsive seizures than during times that are seizure-free.
- To examine correlation of study drug dose and fever-induced convulsive seizure frequency, severity, and duration.
- To examine the timing of diary-reported events vs. automatically detected events.
- To assess quality of life while using the Embrace system with the following measures:
  - Quality of Life (QoL) of the parent/caregiver using the EQ-5D-5L scale.
  - Affective symptoms of the parent/caregiver using the Hospital Anxiety and Depression Scale (HADS).
- To assess caregiver stress using the Perceived Stress Scale (PSS).

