- For each seizure, the peri-ictal EDA recording will be segmented from 60 minutes before detected seizure onset to 120 minutes afterward. A “significant EDA response” is declared when an increase in skin conductance level of more than 2 times the standard deviation of the pre-ictal baseline occurs. The time of the beginning of such an EDA response is defined as “EDA\_start,” the time of the maximum peak of the EDA response is defined as “EDA\_peak,” and the point in time following this peak, when the EDA falls below 10% of the peak amplitude is defined as “EDA\_end.” Significant EDA responses will be analyzed in terms of the amplitude of their EDA\_peak, the response duration, defined as the difference between “EDA\_end” and “EDA\_start,” and the natural logarithm of the area under the curve (AUC) of the rising phase (from “EDA\_start” to “EDA\_peak”) and of the total response (from “EDA\_start” to “EDA\_end”), ie, LogAUCrise and LogAUCtot. These measures will be examined to see if they vary over time with the treatment. Each of the measures will be evaluated for changes over time using a mixed model repeated measures (MMRE) that allows for a different intercepts for each subject (ie, a random effect) but a common slope over time (ie, a fixed effect).
- Skin-surface temperature changes will be averaged daily and compared over time, with separate comparisons made for “seizure-free” periods and for “pre-seizure periods.” The duration of these periods will be based on average 60-minute intervals, but may also be examined more with shorter intervals. Changes in skin-surface temperature over time will be evaluated using similar MMREs as described above for EDA endpoints.

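### EDA response size is analysed only in seizures detected with the help of EDA, and then only in responses above 2 SD, so a true fall would be attenuated, and the watch count could fall without fewer seizures

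*Combined protocol and SAP*

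**What the plan says.** Section 2.2 sets a directional secondary exploratory objective: "To examine if the size of the electrodermal activity (EDA) response during and after a convulsive seizure is reduced over time with ZX008 treatment".

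The Synopsis (Statistical Methods) and Section 8.4 describe the sample for it differently. The Synopsis has "For each seizure detected by the Embrace watch, the peri-ictal EDA recording will be segmented from 60 minutes before detected seizure onset". Section 8.4 has "For each seizure, the peri-ictal EDA recording will be segmented from 60 minutes before detected seizure onset to 120 minutes afterward". Section 8.4 drops the restriction to watch detections but still places the window by detected onset, so a seizure that the watch misses has no defined window.

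Section 1.2 describes the detector: "The Embrace watch monitors electrodermal activity (EDA) and accelerometer-sensed changes in motion to analyze the information and detect patterns". The documents give neither the weights of the two signals nor a threshold.

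Both sections then apply a second condition. A response counts as significant only if it is "declared when an increase in skin conductance level of more than 2 times the standard deviation of the pre-ictal baseline occurs", and the size measures are computed on those responses: "Significant EDA responses will be analyzed in terms of the amplitude of their" peak, their duration and their log areas. Section 8.4 models each measure over time with a random intercept per subject and one common slope. No term concerns detection or the response rule.

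The caregiver's ERT diary runs in parallel (Section 3.1). Section 8.4 compares watch and diary counts by Spearman rank correlation; the Synopsis names Cohen's kappa. One item, in the Synopsis only, correlates the number, severity and duration of watch-detected seizures with study drug dose and makes no use of the diary count.

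**The concern.** The objective asks whether EDA responses shrink on treatment. If they do, the seizures with the smallest responses are the ones most likely to be missed by a detector that uses EDA, and also the ones most likely to fail the 2 SD rule. Both steps remove small responses, and remove more of them later than earlier, so the mean of what remains falls less than the truth. A mixed model fitted to the retained responses cannot recover what was removed.

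The first step has a side effect. Falling EDA lowers the sensitivity of the watch, so its seizure count drops even if seizures are constant. Dose is titrated upward from the start of the extension, so a loss of detection with time could look like a dose relation in the Synopsis fever and dose item.

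**Working it through.** The documents state no sensitivity, EDA variance or effect size, so there is no figure of the plan's to reproduce. All numerical inputs below are assumptions.

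**Model for detection**

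- Log EDA amplitude X is normal with mean 0 and SD s (0.7 or 1.0) at the start, and mean ln(1 − f) later, where f is the true fall (30% or 50%).
- Probability of detection = 1/(1 + exp(−(a + bX))), with b = 1 to 3 per log unit and a chosen so that initial sensitivity is 80%.
- The true number of seizures is constant.
- Observed fall = 1 − exp(later mean of X among detected − initial mean of X among detected).
- Fall in watch count = 1 − later sensitivity/0.80.

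**One case in full** (s = 1.0, b = 1, f = 30%). The shift is ln 0.7 = −0.357, and a = 1.65 gives 80% sensitivity. The mean of X among detected seizures is 0.173 initially and −0.141 later, a difference of −0.314. The observed fall is 1 − exp(−0.314) = 26.9%. Sensitivity drops to 74.7%, and the watch count falls by 1 − 0.7465/0.80 = 6.7%.

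**Detected seizures only, no 2 SD rule**

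| True fall | b per log unit | Fall seen | Later sensitivity | Watch-count fall |
|---|---|---|---|---|
| 30% | 0 (motion only) | 30% | 80% | 0% |
| 30% | 0.5 | 29.1–29.5% | 77% | about 3.7% |
| 30% | 1 to 3 | 20.8–28.2% | 67–75% | 6.7–15.8% |
| 50% | 1 to 3 | 35.2–47.3% | 53–69% | 13.9–33.5% |

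A separate simulation with other assumptions (SD 0.6 or 1.0, initial sensitivity 70% or 90%, slope 0 to 4 per SD of log EDA) agrees in direction. A true 30% fall is seen as 26–28% at slope 1 and 17–23% at slope 4, with no bias at slope 0.

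**Adding the 2 SD rule.** It is mimicked by a fixed amplitude cut that removes the lowest 1%, 5%, 10% or 20% of initial responses. The true fall is 30%, initial sensitivity 80%, and b = 1 to 3.

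| Cut | Every seizure included | Detected seizures only |
|---|---|---|
| 1% | 27.4–27.7% | 20.8–26.7% |
| 5% | 23.2–23.8% | 20.4–23.4% |
| 10% | 20.3–21.0% | 19.4–21.1% |
| 20% | 16.7–17.3% | 16.6–17.6% |

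The middle column is the effect of the response rule by itself. Once it removes about 10% or more, selection by the detector adds almost nothing to the attenuation. With a cut of 1% the detector is the main source of bias. The rule does not alter the watch-count result, which comes from detection alone.

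**Would the planned comparison reveal the loss?** If every subject's watch count in a period is multiplied by the same factor, the ranks across subjects do not change, and neither does the Spearman correlation with the diary for that period. A uniform loss of sensitivity therefore passes unseen.

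**The case against.** Several arguments on the other side have force.

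- *Motion is also a detector signal, and the weights are unknown.* This stands. A reader might infer that seizures with weak EDA must drop out and that a fall would be hidden. The documents do not support that. Motion can still trigger detection, the bias is zero if motion alone decides, and in every case computed the fall is reduced but still present.
- *The response rule dominates, so changing only which seizures enter would achieve little.* This stands at cuts of about 10% or more. The two selections need to be handled together.
- *The diary guards against misreading the count.* This stands in part. A reader might infer that lost detection would be taken for a treatment effect on seizures. The diary count does not depend on the detector in this way, Section 8.4 sets the watch against it, and Section 1.2 foresees comparison of undetected seizures with the diary. But rank correlation does not measure a common loss of sensitivity, and the Synopsis fever and dose item has no diary check.
- *The diary is not an independent reference.* This stands. The Alert app phones or texts caregivers, who keep the diary, so detected seizures are more likely to be entered. Unwitnessed seizures that the watch misses are in neither record.
- *This is one exploratory objective in a pilot of up to 20 subjects, with ease of use as the primary criterion and full methods left to a later SAP.* This limits the importance. It also means that the change can still be made, since Section 8.4 has the SAP finalised before database lock.

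**Conclusion.** The point holds as a bias of known direction and unknown size. If EDA carries any positive weight in detection, restriction to detected seizures pulls the EDA slope toward no change and can lower the Embrace count, but not the diary count, without fewer seizures. The figures of 21% to 28% seen for a true 30%, and a watch-count fall of 7% to 16%, rest on 80% initial sensitivity, log SD 0.7 to 1.0 and log-odds slopes of 1 to 3. They describe the detector step alone, not the whole planned analysis.

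With the response rule in place at an assumed 10% to 20% cut, a true 30% fall is seen as about 17% to 21% whether or not missed seizures are added. A flat or shallow EDA trend from the planned analysis would therefore be weak evidence that EDA responses are unchanged. The change is worth making, though it bears on a secondary exploratory objective only.

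**What to change.** 1. Reconcile the Synopsis and Section 8.4 on which seizures enter the EDA analysis.
2. Segment EDA also around diary-reported convulsive seizures that fall in worn, recorded time and that the watch missed. Onset can be taken from the stored motion trace near the diary time.
3. Keep non-significant responses in the size analysis, either as measured or by reporting the proportion significant over time beside the size of significant ones. Step 2 without this step recovers little.
4. Keep the detected-only, significant-only analysis as a sensitivity analysis.
5. Report the share of diary seizures detected, by 28-day period, beside the Embrace counts.
6. Do not interpret changes in watch count with dose (the Synopsis fever and dose item) without the diary count.

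If every seizure could be measured and all responses kept, the model above would return the true 30% or 50% by construction. In practice that depends on accurate diary times and on wear.

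The cost is SAP wording and extra programming on raw data that Sections 6.2.2.1 and 9 already have stored. Some diary seizures will not be found in the trace and must be listed. Because alerts prompt diary entries, the share detected may be too high, and seizures in neither record remain a stated limitation.
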